Awareness and Self-Compassion Enhancing Narcolepsy Treatment (ASCENT)

NCT04306952

11/14/2018

Protocol

Overview of Research Plan

The overall approach taken for this R34 follows recommendations for early stage treatmentdevelopment activities aimed at establishing the parameters of the intervention and research protocols before conducting a full-scale randomized controlled trial (RCT). Building upon our preliminary data, this project focuses on treatment-development, recruitment, and assessment by conducting a feasibility trial to determine the optimal parameters for adapting and delivering an MBI for people with narcolepsy. The first phase of this project consists of preparatory activities, including completion of the study protocol and training of treatment providers. Phase II consists of a feasibility trial in which 60 individuals will be randomized to receive one of three MBI doses of varying length: 4-week MBI (short), 8-week MBI (standard), or 12-week MBI (extended). All MBIs will feature similar content and structure and will be delivered in groups (n=4) using live videoconferencing.

Phase I: Protocol refinement and training of MBI Providers

The main goal of Phase I is to prepare for the feasibility trial. Preparatory activities include refining and completing the MBI protocols, developing a manual of operations, establishing a data and safety monitoring plan, and obtaining IRB approval. We have a preliminary outline of the three MBI doses that will be developed into a formal treatment manual that can be used for training and delivery.

MBI Provider Training. The next step is to recruit and train at least 6 MBI providers. The purpose of this step is to determine the feasibility of recruiting MBI providers for a large-scale study and to evaluate the level of training needed for providers to work effectively with people with narcolepsy (see Specific Aim 1). We will select providers who have experience in delivering a traditional MBI, such as MBSR or MBCT, and who have a personal mindfulness meditation practice but do not have to be licensed clinicians (e.g., psychologist, social workers). This is consistent with the requirements for MBSR and MBCT, which should enhance the potential pool of providers. We will then provide training workshops, providing education on narcolepsy and the challenges that patients have described. We will also provide training on delivering each of the MBI doses (see C.8. and Table 3 below), emphasizing the adaptations from traditional MBIs and the application of mindfulness principles to working with symptoms of narcolepsy. Based on feedback from our focus groups (see C.2), we will educate providers on the symptoms of narcolepsy as well as the unique challenges that are common among people with narcolepsy (e.g., stigma, negative public perception, unpredictability of symptoms). We expect to conduct workshops via video-conferencing to enhance flexibility in recruiting MBI providers, but will also conduct these in-person for those who are in the local area. Each provider will be required to demonstrate competency in delivering the MBI protocols based on evaluation by the PI or Co-I. We will also gather input from MBI providers regarding the intervention and finalize the MBI protocols. The major milestones of this phase are to finalize the manual of operations for the study protocol, establish a treatment manual for each MBI dose, and train 6 MBI providers to deliver MBI.

Phase II: Feasibility Trial

Phase II consists of a feasibility trial to gather data on the feasibility, acceptability, and clinical impact of MBI. Participants will be randomly assigned to receive one of three MBI doses (short, standard, or extended course) to determine the optimal parameters for length of the MBI program for people with narcolepsy. An important consideration at this stage is to optimize clinical impact and acceptability with cost-effectiveness as a secondary consideration in determining the optimal MBI dose. All MBIs will be delivered in small groups (n=4) using live videoconferencing. Recruitment and screening will begin upon completion of Phase I (month 6)

and we anticipate running 5 cycles. Given the focus on optimization, we will conduct an interim review after completing Cycle 2 to evaluate the need for modifications to the MBI protocol or study protocol. We plan to complete the interventions and assessment in Year 3, between months 6 to 8, leaving the remaining time for data analysis, dissemination of results, and preparation of a U01 or R61/R33 application depending on the findings of this study.

Short MBI (4-week). The short MBI consists of four weekly group sessions that are two hours each and follows the structure and format described above for each group and home meditation practice. Meta-analytic results of MBIs in lifestyle medicine trials have found that intervention effects are not dependent on the length of the MBI and that shorter-length MBIs (< 8 weeks) have demonstrated positive findings with effect sizes similar to MBI of 8 weeks or longer. Therefore, the rationale for testing the short MBI is to evaluate a low-dose (8 hours of contact) MBI that optimizes cost-effectiveness and minimizes patient burden.

Standard MBI (8-week). The standard MBI consists of eight weekly group sessions that are approximately two hours each. Group sessions will follow the structure and format described above. The length of this package is based on the standard length of MBSR as an 8-week program. The rationale for testing the standard MBI is to provide a comparison to a dose (16 hours of contact) that is most similar to the length of MBSR and has the fewest modifications, making it easier to train MBI providers.

Extended MBI (12-week). The extended MBI consists of four weekly group sessions followed by four group sessions every other week over the course of 12 weeks. Each group session will be two hours and follows the contents and structure described above. The group sessions will be identical to the standard package except for the timing (every other week) of the last four sessions. In addition to the group sessions, the MBI provider will offer "office hours" in between the bi-weekly group sessions, where participants will be able to schedule individual sessions with the MBI provider to discuss questions and troubleshoot their mindfulness practice. The rationale for testing the extended MBI is to optimize acceptability and uptake based on our focus group data by allowing for a slower, extended pace of learning mindfulness practices with an opportunity to have individual discussions with the instructor (16 hours of contact + individual office hours).

Data Analysis Plan

Overall Approach and Power Considerations. The overall goal of this project is to work out the parameters of a mindfulness program that will be feasible and acceptable for people with narcolepsy. Following recommendations for pilot studies, this stage of testing focuses on evaluation of benchmarks and refinement of the intervention, recruitment methods, and assessment protocol. Formal hypothesis testing of outcomes and clinical endpoints will be conducted at a later stage, once the optimal MBI dose and delivery format is selected and refined. Since sex is not a biological variable of key interest in this study, we plan to conduct all analyses aggregated across sex. However, if patterns emerge to indicate that sex could influence the results, we will explore post-hoc analyses as needed (e.g., sex as a covariate). As suggested for pilot studies, our sample size was selected based on balancing the research priorities established in the specific aims with the pragmatics of recruitment and the resources allowed in the R34 funding mechanism. Data gathered on recruitment pace and effect size on clinical measures will be used to inform power considerations and the feasibility of conducting a large-scale trial in future studies. A summary of the analytic plan is described below. See Statistical Design and Power for details about specific analyses and the data management plan.

Specific Aim 1. Determine the feasibility and acceptability of MBI using videoconferencing for the purpose of improving psychosocial functioning in people with narcolepsy. To carry out Aim 1, we will evaluate the short, standard, and extended doses of MBI on the pre-determined benchmarks below to determine the feasibility and acceptability.

- Benchmark 1 (feasibility of MBI providers): Recruit and train at least 6 qualified providers to deliver the MBI conditions (see section C.4. for details). No specific analyses are planned for this benchmark.
- Benchmark 2 (acceptability of MBI doses): An average attendance ≥ 80% of sessions per MBI condition will be used as a benchmark for determining acceptability of the videoconference delivery of MBI and patient uptake of MBI. This benchmark corresponds to attendance of all sessions (4 out of 4) for the short MBI and 7 out of 8 sessions for the standard MBI. For extended MBI, participants must attend at least 6 out of 8 group sessions plus at least one optional individual session scheduled during provider "office hours" or 7 out of 8 group sessions if no individual sessions are scheduled.
- Benchmark 3 (receipt of MBI targets): The benchmark for receipt of mindfulness and self-compassion will be an increase from baseline to post-treatment in the SCS and FFMQ with an effect size in the moderate range or higher (Cohen's *d* ≥ .5) per MBI dose. This benchmark will be used to evaluate the feasibility that people with narcolepsy are capable of acquiring self-compassion and mindfulness skills from the MBI and also provide estimations of the effect size for each MBI dose (4, 8, 12 weeks). Given that our conceptual model (see Figure 1) posits that self-compassion, mindful awareness, and mindful action are key putative mechanisms by which MBI improves HRQOL, this benchmark will provide an initial test of our conceptual model.
- Benchmark 4 (feasibility of clinical impact): We will use a similar benchmark (*d* ≥ .5) to evaluate the clinical impact from baseline to post-treatment for each MBI dose on the PROMIS global health, depression, anxiety, and psychosocial illness impact measures.

Secondary Considerations. In addition to these benchmarks, we will conduct other analyses as secondary considerations of acceptability and feasibility. We will examine the amount of meditation practice from the daily diaries (total minutes of practice and number of sessions) to assess enactment of mindfulness meditation outside of the sessions. We will conduct qualitative analyses from focus group data using thematic analysis to evaluate themes and patient feedback on each MBI dose. We will also conduct exit interviews with the MBI providers to gather input from the provider's perspective as to the optimal MBI dose. In addition to evaluating effect sizes at post-treatment (Benchmark 3 & 4), we will also conduct linear mixed models to examine the trend of each MBI dose over time (A1 to A4) on SCS, FFMQ, and exploratory clinical measures (ESS, FOSQ, sleep/wake patterns from actigraphy and sleep diaries, neurocognitive assessment). These exploratory analyses will be used to supplement the evaluation of the effect sizes given the variation in time at post-treatment across MBI doses. We will also review adverse events and consider the potential harms as a factor in selecting the MBI condition (i.e., least AEs will be selected). Finally, we will consider the cost-effectiveness of each MBI dose (number of sessions, amount of face-to-face contact, amount of provider training).

Selecting the optimal MBI dose. The major milestone of Specific Aim 1 is to select the optimal MBI condition using the parameters described above. We anticipate that each MBI dose will have a unique profile (e.g., short MBI will have high attendance but smaller effect size on SCS and FFMQ) and will select the MBI dose that is able to achieve the most benchmarks. If these benchmarks cannot determine a condition that is superior, we will use secondary considerations and cost-effectiveness (lowest-level of resources) to determine the optimal MBI dose. This MBI program will be used for further testing or optimization (see Future Directions).

Specific Aim 2: Determine the feasibility of recruitment and assessment methods for MBI using videoconferencing. The purpose of Aim 2 is to evaluate the pace of recruitment and the feasibility of remote data collection using the assessment instruments proposed for conducting a future large-scale trial. We will use the following benchmarks to carry out Aim 2:

- Benchmark 5 (recruitment feasibility): The benchmark for feasibility of recruitment will be enrollment of 12 participants who meet all eligibility criteria per 3-month cycle (or ≥ 4 participants per month). The criteria for this benchmark is based on the minimum rate of recruitment needed to support randomization into groups of four for each of the MBI conditions. It will provide data to inform recruitment decisions, the method of randomization, and the number of sites needed for a large-scale study in the future.
- Benchmark 6 (assessment feasibility): The benchmark for the assessment protocol is complete data for ≥ 80% of all participants (n=48 out of 60). Completion is defined as providing valid data from baseline (A1) through post-treatment for each MBI. This benchmark will inform the degree of missing data, the acceptability of the assessment protocol (e.g., neuropsychological assessment via videoconferencing), and the selection of instruments (e.g., reliability of collecting actigraphy data remotely).

Secondary considerations. In addition to these benchmarks, we will evaluate the assessment instruments for inclusion in future studies by reviewing the effect size, costs, and patient feedback from focus groups for each instrument. For example, if there is evidence that some PROMIS domains selected for this study are not relevant we will not include these in future studies. We will also examine issues such as practice effects or fatigue to evaluate the validity and feasibility of conducting the neurocognitive battery using videoconferencing for people with narcolepsy. The major milestone of Aim 2 is to establish operational guidelines for effective recruitment methods and an assessment protocol that can be used to support a future large-scale trial.

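### Benchmark 2 treats an arm average of at least 80% attendance as the same thing as whole-session counts for one participant; the two differ and can give opposite verdicts

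*Combined protocol and SAP*

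**What the plan says.** All of this is in the Data Analysis Plan, Specific Aim 1, unless noted.

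- Benchmark 2 opens with a rule at the level of the arm: "An average attendance ≥ 80% of sessions per MBI condition will be used as a benchmark".
- The next sentence translates that rule into sessions for two arms. It "corresponds to attendance of all sessions (4 out of 4) for the short MBI and 7 out of 8 sessions for the standard MBI".
- The extended arm has its own sentence, worded for individuals: "participants must attend at least 6 out of 8 group sessions plus at least one optional individual session", "or 7 out of 8 group sessions if no individual sessions are scheduled".
- Under the paragraph on selecting the optimal dose, the investigators "will select the MBI dose that is able to achieve the most benchmarks". If the benchmarks do not separate the doses, secondary considerations and cost-effectiveness decide.
- Contact time differs by dose. The short arm is described as a "low-dose (8 hours of contact) MBI", the standard arm has 16 hours, and the extended arm has "16 hours of contact + individual office hours" (Phase II: Feasibility Trial).
- The overview of the analysis points elsewhere for detail: "See Statistical Design and Power for details about specific analyses and the data management plan". No section of that name is in the document.

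**The concern.** A mean over an arm need not be a whole number, so rounding up to whole sessions has no place in it. The counts 4 and 7 are what one person needs in order to have attended at least 80%. The plan therefore offers two different statistics as one benchmark: the arm's mean attendance, and whether a participant reaches a count. It does not say which decides. If the counts decide, it does not say what share of participants must reach them. Benchmark 6, by contrast, does state such a share (48 of 60).

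The benchmarks are the decision rule here, because formal hypothesis testing is deferred to a later study. Only Benchmarks 2, 3 and 4 are scored dose by dose; 1, 5 and 6 concern providers, recruitment and data completeness for the trial as a whole. With three scored items per dose, one changed verdict on attendance can make or break a tie.

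**Working it through.** **Inputs.** Sessions: 4 (short), 8 (standard), 8 group sessions plus optional office hours (extended), from the dose descriptions. Participants: 60 randomised to 3 doses, so 60/3 = 20 per arm. This agrees with 5 cycles of one group of 4 per dose. Person-sessions: 20 × 4 = 80 (short), 20 × 8 = 160 (standard).

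**Step 1. Reproduce the plan's counts.** As an arm mean, 0.80 × 4 = 3.2 and 0.80 × 8 = 6.4. These do not give 4 and 7. Rounding up for one person does: 3.2 becomes 4 (4/4 = 100%) and 6.4 becomes 7 (7/8 = 87.5%). The stated counts are reproduced only as a per-participant threshold.

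**Step 2. Average met, count mostly not.**
- Short, 4 people at 4/4 and 16 at 3/4: (16 + 48)/80 = 80%; 4/20 = 20% reach the count.
- Standard, 4 at 8/8 and 16 at 6/8: (32 + 96)/160 = 80%; 4/20 = 20% reach it.

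**Step 3. Count mostly met, average not.**
- Short, 15 at 4/4 and 5 at 0/4: 60/80 = 75%; 15/20 = 75% reach the count.
- Standard, 18 at 7/8 and 2 at 0/8: 126/160 = 78.75%; 18/20 = 90% reach it.

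**Step 4. Range at a mean of exactly 80%.** Let x be the number reaching the count.
- Short: 4x ≤ 64 ≤ 4x + 3(20 − x), so x runs from 4 to 16 (20% to 80%).
- Standard: 7x ≤ 128 ≤ 8x + 6(20 − x), so x runs from 4 to 18 (20% to 90%).

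**Step 5. Extended arm, everyone at six group sessions plus one individual session.**
- Group sessions only: 6/8 = 75%, below the bar.
- Individual session added to numerator and denominator: 7/9 = 77.8%, below.
- Individual session replaces one missed group session: 7/8 = 87.5%, above.

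**Step 6. Can selection change?** This is an illustration, not a forecast. Assume an 80% required share for the count, which the plan does not state.
- Short, 12 at 4/4 and 8 at 3/4: (48 + 24)/80 = 90%; 12/20 = 60% reach the count.
- Standard, all 20 at 7/8: 140/160 = 87.5%; 100% reach the count.

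Both pass on the average, but short fails on the count although its mean attendance is higher. Suppose further that both doses meet Benchmarks 3 and 4, that extended meets fewer benchmarks, and that each benchmark counts once. The average then gives a 3–3 tie, which goes to secondary considerations and cost (8 against 16 contact hours). The count gives standard the selection, 3 to 2.

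**Step 7. Is this confined to contrived patterns?** Assume each person attends each session independently with probability p, and again an 80% required share (16 of 20) for the count. The mean rule is P(at least 64 of 80) for short and P(at least 128 of 160) for standard.

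| p | Short: mean passes | Short: count passes | Standard: mean passes | Standard: count passes |
|---|---|---|---|---|
| 0.80 | 0.57 | 0.0004 | 0.55 | 0.006 |
| 0.85 | 0.92 | 0.010 | 0.97 | 0.13 |
| 0.90 | 0.998 | 0.13 | >0.999 | 0.69 |

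At p = 0.85 the chance that one person reaches the count is 0.85⁴ = 0.52 (short) and 8 × 0.85⁷ × 0.15 + 0.85⁸ = 0.66 (standard). Independence is a strong assumption: if absences cluster in a few people, the gap narrows.

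**The case against.** The counts have a sensible origin. They are the smallest whole numbers of sessions at or above 80% for one person, and may have been meant only to help the reader. That explains them, but it does not make them equivalent to an arm mean, and the extended sentence is worded as a requirement.

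A reader might infer that the extended rule contradicts the 80% bar outright, because six of eight group sessions is 75%. The documents do not support that. The benchmark speaks of sessions, not group sessions, and office hours are part of that dose. The two routes (six plus one, or seven) both total seven, so substitution, giving 87.5%, is arguably the natural reading. What stands is that the scoring is not stated. Nor does the plan call the extended condition an equivalent of 80%; it says so only of the short and standard counts.

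The hand-built patterns in Steps 2 and 3 are extreme. They prove that the readings can disagree, not how often. Step 7 suggests that disagreement does not need extreme patterns, but only under its assumptions.

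That the short arm's count allows no missed session follows from having four sessions; any per-person rule of at least 80% does this. It is not an error in itself, but it is a reason not to let the count stand in for the mean.

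The analysis text describes itself as a summary, and the section it cites may define the scoring. It is therefore not established that the sponsor lacks a rule. The sentence in Benchmark 2 would still be wrong as it stands.

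Finally, this is a feasibility trial with a review after Cycle 2 that can change the protocol. That limits the stakes and makes correction easy.

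**Conclusion.** The point holds as a wrong equivalence in a decision threshold, together with an unstated scoring rule for the extended arm's individual session. At a mean of exactly 80%, the share of participants reaching the stated count can lie anywhere from 20% to 80% (short) or 20% to 90% (standard). The two readings can disagree in either direction. The extended arm at six plus one can fail or pass according to how the session is counted.

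These results rest on 20 participants per arm and simple counting. The effect on dose selection rests on more: an assumed 80% share, one point per benchmark, and assumed results on Benchmarks 3 and 4. It shows that selection can change, not that it will.

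A reader might also infer that 4 of 4 and 7 of 8 are bars for the whole arm, so that a single absence among 20 people fails the short dose. The documents do not support this. The counts are plainly one person's 80% rounded up, and the plan itself expects high attendance in the short arm, which fits poorly with a bar allowing no absence.

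The text should be corrected before attendance is scored.

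**What to change.** 1. Keep the arm mean of at least 80% as the single governing rule for Benchmark 2.
2. Delete the statement that this equals 4 of 4 and 7 of 8, or relabel those counts as a descriptive result: the share of participants in each arm who attended at least 80% of sessions.
3. Define attendance in the extended arm so that the credit for an individual session is scored consistently. For example, one individual session may replace at most one missed group session per participant, with the denominator kept at 8. This preserves the sponsor's six-plus-one route within a mean. Report attendance at group sessions alone beside it.
4. If the counts are meant to govern instead, say so and state the share of participants per arm who must reach them.
5. Check the result against the cited Statistical Design and Power section so that the two agree.

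The cost is wording only, with no new data. The one small drawback is that the extended arm's credit has to be expressed within a mean rather than as a count.

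### Home practice is assessed as totals although the doses last 4, 8 and 12 weeks; a weekly rate and a stated diary window are needed before doses are compared on it

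*Combined protocol and SAP*

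**What the plan says.** The Overview of Research Plan randomises 60 people to "4-week MBI (short), 8-week MBI (standard), or 12-week MBI (extended"). The extended dose reaches 12 weeks through "four weekly group sessions followed by four group sessions every other week over the course of 12 weeks". Home practice is part of the intervention: the short dose "follows the structure and format described above for each group and home meditation practice". The description that this points back to is not in the supplied text, so no practice target is available.

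The measure of home practice and its purpose are given under Specific Aim 1, Secondary Considerations, as "amount of meditation practice from the daily diaries (total minutes of practice and number of sessions) to assess enactment of mindfulness meditation outside of the" group meetings. It is not a benchmark. It belongs to a list introduced with "In addition to these benchmarks, we will conduct other analyses as secondary considerations of acceptability and feasibility".

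Under Selecting the optimal MBI dose, the investigators "will select the MBI dose that is able to achieve the most benchmarks". The list comes into play at the next step: "If these benchmarks cannot determine a condition that is superior, we will use secondary considerations and cost-effectiveness", the latter meaning the lowest level of resources.

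**The concern.** Enactment is a behaviour: how much people practise while they are in the programme. A sum over the programme mixes that behaviour with the length of the calendar, and calendar length is exactly what differs between the arms. A longer dose can show more total practice even when its participants practise less per day.

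The plan allows for unequal length or session number elsewhere. Benchmark 2 scores attendance as a percentage of sessions, not as a count. The mixed models over A1 to A4 are justified by the fact that post-treatment falls at different times across doses. Home practice has no matching adjustment in the supplied text.

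Two things are at stake. Practice can enter the choice of dose when the benchmarks leave a tie. It is also the only stated measure of practice outside sessions, so a reader of the results would naturally set the three totals side by side.

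**Working it through.** **Inputs**

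- Programme lengths: 4, 8 and 12 weeks, or 28, 56 and 84 days (Overview of Research Plan).
- Measure: summed minutes and a count of practice sessions (Secondary Considerations).
- Diary window: not stated. The main case assumes that diaries run through each dose's own programme.
- Minutes per day: not stated. 10, 20 and 30 are assumed, to show the range.

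**The plan's own figures.** Extended dose: 4 × 1 week + 4 × 2 weeks = 12 weeks, as stated. Contact hours: 4 × 2 = 8, 8 × 2 = 16 and (4 + 4) × 2 = 16, as stated. The plan gives no figure for home practice.

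**Totals under equal daily practice.** Total = minutes per day × programme days. Rate = total ÷ programme weeks.

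| Assumed min/day | Short total | Standard total | Extended total | Ratio | Rate in every arm |
|---|---|---|---|---|---|
| 10 | 280 | 560 | 840 | 1:2:3 | 70 min/week |
| 20 | 560 | 1,120 | 1,680 | 1:2:3 | 140 min/week |
| 30 | 840 | 1,680 | 2,520 | 1:2:3 | 210 min/week |

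The ratio does not depend on the assumed minutes. A count of practice sessions summed over the programme scales in the same way.

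**Reversal of ranking.** A dose shows the higher total once its daily practice, as a share of the comparator's, exceeds the inverse ratio of days:

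- extended against short: 28/84 = one third;
- standard against short: 28/56 = one half;
- extended against standard: 56/84 = two thirds.

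For example, 30 min/day in the short dose totals 30 × 28 = 840 minutes, and 12 min/day in the extended dose totals 12 × 84 = 1,008. The total ranks the extended dose higher although its daily practice is 12/30 = 40% of the short dose's.

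**Other diary windows.** If every arm kept diaries for the same fixed window (7, 14 or 28 days), equal daily practice would give totals of 1:1:1 and the artefact would vanish.

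**Could the measure reach the decision?** Benchmark 1 is met or missed for the whole trial, so within Aim 1 only Benchmarks 2, 3 and 4 can differ by dose, and each dose scores 0 to 3. For illustration, assume independent benchmarks, the same pass probability p for every dose, and one point per benchmark. Then P(tie for first) = 1 − 3 × Σ P(score = k) × P(score < k)². At p = 0.5 the scores 0, 1, 2, 3 have probabilities 1/8, 3/8, 3/8, 1/8. The sum is 3/8 × (1/8)² + 3/8 × (4/8)² + 1/8 × (7/8)² = 0.195, and the tie probability is 1 − 0.586 = 41%. The same formula gives 49% at p = 0.7 and 62% at p = 0.8. These figures rest wholly on the assumptions; they show only that a tie is not remote.

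**The case against.** The strongest case on the other side has five parts.

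- **The diary window is unknown.** The factor of three needs diaries that span each programme. The supplied text does not say so, and a common window removes the effect. The Data Analysis Plan also refers to a Statistical Design and Power section that was not supplied and may define a window or a rate. This stands, and makes the size conditional.
- **No ranking by totals is written down.** The plan says it will examine practice. It states no rule that more is better, although it does give a direction for adverse events and for resources. The period over which practice sessions are counted is also open. This stands as to wording. Even so, a measure that helps choose among three doses has to be compared across them in some form.
- **The dose choice is not shown to be distorted.** A reader might infer that the totals tilt the trial towards the 12-week dose. The documents do not support that. Practice is in no benchmark. In a tie it is one unweighted item beside focus groups, provider interviews, mixed models and adverse events, with cost-effectiveness as well. Lowest resources favours the short dose (8 contact hours against 16), and a raw count of adverse events, if collected over each programme, would do so too.
- **Nothing is lost.** A reader might infer that the plan cannot show whether length or pace affects practice. That also goes too far: the data are daily diaries and programme lengths are fixed, so a rate can be recovered by division. What is missing is the commitment to report it.
- **Totals have a proper use.** Cumulative exposure is a fair description when programme length is the factor varied. This stands, and the totals should be kept.

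None of this makes an unscaled total a sound between-dose measure of a behaviour.

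**Conclusion.** The point holds in a limited form. As written, home practice is assessed by totals across doses of 4, 8 and 12 weeks, with no rate and no stated diary window. If diaries cover each programme, equal daily practice gives totals of 1:2:3 at any daily amount, and the ranking can reverse. Totals would then be unsuitable for comparing enactment between doses, and they could mislead where the benchmarks tie.

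The conclusion rests on the diary window being the programme, and on no rate being defined in the section that was not supplied. It does not extend to a net bias in dose selection. This is a gap in the definition of one possible tie-break item. It is worth closing because closing it is cheap.

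**What to change.** In Secondary Considerations under Specific Aim 1:

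1. State the diary window for each dose.
2. Beside the totals, report mean minutes per week and practice sessions per week, each calculated as (sum over returned diary days ÷ number of returned diary days) × 7. Do this over each dose's programme weeks.
3. Report the same rates for weeks 1–4, when all three doses have weekly group sessions. This gives a common period. It cannot test the extended dose's slower pace, because the standard and extended schedules differ only after week 4.
4. Use the rates for any between-dose comparison of enactment, including in a tie, and label the totals as cumulative exposure.
5. Show diary completion by arm, with a sensitivity version that counts missing diary days as no practice.

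The cost is a few sentences of analysis wording, with no new data if diaries are kept through the programme. The downside is that a rate per returned day overstates practice if people skip the diary on days without practice. As a hypothetical case, take 20 minutes on 14 of 28 days, with diaries returned only for those 14 days. The total is 20 × 14 = 280 minutes. The returned-day rate is 280/14 × 7 = 140 min/week, and counting missing days as zero gives 280/28 × 7 = 70 min/week. If unreturned days hold no more practice per day than returned ones, the two versions bracket the truth, which is why both are needed.
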